- 3. * Describe the study's background and significance, including citations, or upload a citation list in document upload. Use lay language whenever possible.

Patients with cirrhosis have difficulties with their sleep quality, which adversely affects their health-related quality of life1. It is assumed the sleep disturbances are related to hepatic encephalopathy (HE) in these patients2. However, several recent reports have indicated that this is not a perfect concordance and that cognition is not related to sleep disturbance. 1.3. The mechanism for this change is not clear, although there is evidence of melation-delayed phase in these patients as well as difficulties with the excretion pattern of cortisol4. Ghrelin is an orexigenic hormone produced by the stomach which stimulates the appetite and also has a profound effect on sleep5, 6. Our group has demonstrated a substantial alteration in ghrelin secretion in cirrhosis that correlates with poor slow-wave sleep7. In healthy individuals, ghrelin injection encourages slow-wave sleep while sleep deprivation increases ghrelin levels6, 8, 9. The role of ghrelin in the sleep disturbances of cirrhosis has not been determined. Prior studies have also lacked the use of overnight polysomnography as a tool and have relied on either actigraphy or questionnaires10. There is a need for detailed mechanistic and therapeutic approaches to analyzing sleep disturbances in cirrhosis. Also the therapy of sleep disturbance in cirrhosis is largely empirical. Prior studies have evaluated hydroxyzine which runs the risk of precipitating HE. Ramelteon is a melation analog that is FDA-approved for use in insomnia and will potentially be useful to restore the sleep-wake cycle in cirrhosis-associated sleep disturbance. We want to study the impact of the FDA-approved ramelteon on the sleep quality (using quesitonnaires and sleep diaries) and duration on these patients with cirrhosis.

Published in Alimentary Pharmacology and Therapeutics ([name] et al 2011 Jul;34(1):103-5) Cirrhotic patients commonly suffer from sleep disturbances and cognitive impairment, but it is unclear whether these are directly related. In healthy controls, ghrelin triggers onset of slow-wave sleep(SWS), and sleep-deprivation(Sdep) increases ghrelin. Aim: To determine whether ghrelin secretion under waking, sleep or Sdep conditions, is altered in cirrhosis, and

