- a description of whether there are any local changes to the protocol s procedures, and if so, what those changes are (i.e. different, omitted, or additional procedures)
- any necessary clarifications of the protocol s content (i.e. what local standard of care or routine practice
- A description of all research measures/tests/interventions that will be used (if applicable)
- A detailed description or list of all secondary data elements and/or secondary specimens that will be obtained and how they will be used (if applicable)

See the help text for additional guidance.

This study will be a prospective study of patients with compensated cirrhosis This study will be divided into screening and post-ramelteon visits

For this study, we will recruit patients with cirrhosis from the hepatology clinic.

Inclusion criteria:

a. Child class A cirrhosis proven by biopsy, radiology or endoscopic evidence of varices b. Able to give informed consent

Exclusion criteria

- a. Diagnosed sleep apnea b. Use of sleep aids
- c. Moderate to severe depression
- d. Unable to give informed consent
- e. Night shift workers
- f. Inter-continental travel within the last 4 weeks
- g. Renal insufficiency on dialysis h. Current alcohol or illicit drug use
- i. Diabetes Mellitus using insulin therapy
- j. Use of chronic hypnotic medications more than once per week or more than 5-6 times per month K. Positive Berlin Questionnaire
- L. Becks Inventory Questionnaire Greater than or equal to 20 without the suicide question. m. Patient unwilling to start therapy
- n. Allergic reactions to ramelteon in the past

Screening: All subjects will come for an initial screening visit to the CRSU at which point the following procedures will be performed

- a Vitals including BMI
- b. Skinfold thickness and waist-hip ratio
- c. Beck Depression Inventory (BDI)
- d. Sickness impact profile for overall HRQOL
- e. Questionnaires regarding sleep
- f Berlin questionnaire
- g. STOP Bang questionnaire
- h. Epworth sleepiness scale (ESS) and i. Pittsburgh sleep quality index (PQSI)

Cirrhotic patients with a Positive Berlin questionnaire will be excluded because these are highly suggestive of sleep disturbances and OSA11, 12. We will also exclude patients who have evidence of moderate to severe depression on Beck Depression Inventory (score ≥20) without the suicide question. They will be paid \$25 for their time.

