All enrolled study participants will perform 5 paper-pencil and two computerized tests of intelligence which will last approximately 35 minutes total. RAMELTEON THERAPY :

The subjects' study chart, current medications, medical history and pregnancy testing will be assessed by [name] and [name] who will then decide if this patient would benefit from ramelteon. The criteria used will be insomnia along with the absence of OSA by the questionnaires. Ramelteon is an FDA-

approved selective melatonin receptor 1 and 2 analog indicated for use in insomnia. The dose used will be 8 mg, the lowest possible dose. If the sleep specialists believe that a particular cirrhotic patient is a candidate for this therapy, they will be clinically prescribed ramelteon after a detailed face to face visit explaining the risks and benefits. Ramelteon is not indicated in patients with severe hepatic impairment (defined as Child Class C), therefore, these patients will not be included in the study.

if the patient agrees to take the medicine, it will be dispensed through the investigational pharmacy, where it will be stored for this study. Patients will be asked to complete a medication and sleep diary for the duration of the drug therapy which will be a maximum of 15 days. Within 15 days of drug initiation, the patients will be asked to complete the sleep questionnaires again and cognitive testing similar to that described in visit 1. They will be paid \$75 for this part of the study.

Date: Tuesday, March 2, 2021 3:54:08 PM

ID: HM13968

Print	Close
-------	-------

View: SF - Bio-Med Project Details

HM13968 - [name] Study of Sleep in Cirrhosis

Bio-Med Project Details

1. 1	Select	all	that	apply	to	this	study	
------	--------	-----	------	-------	----	------	-------	--

~	Drug(s) / Biologics / Supplement(s) / Other Compounds (investigational products or products whose administration is dictated by the study protocol and not per the physician's clinical judgment)
	Bio-Hazards, Other Toxins, Recombinant DNA/Gene Transfer
	Safety and/or effectiveness evaluation of Bio-Medical Device(s), including in-vitro diagnostic devices/assays mobile medical apps, and HUDs used in clinical investigations
	Radiation Exposure and/or Scans involving radiation (eg: PET, MRA, CT, DXA, nuclear medicine, etc)
	Stem Cells
~	Medical or Surgical Procedures (eg physical exam, clinical procedures, scans, etc)
~	Protected Health Information (PHI)
_	None of the Above

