type (e.g., gift card, cash, check, merchandise, drawing, extra class credit)
how it will be disbursed

Screening visit failure: \$25
Screening and initiation of rametteon visit: \$25
Post-rametteon visit: \$75

For patients : total payment for treatment visits and post-treatment sleep visit:is \$100.

 If compensation will be pro-rated, explain the payment schedule For patients : total for treatment visits and post-treatment sleep visit: \$100 will only be paid after return of the Fitbit as a lumpsum

If patients lose their Fitbit device or do not return with it, then the device itself will be considered their payment.

Date: Tuesday, March 2, 2021 4:00:12 PM

ID: HM13968

View: SF - Risks, Discomforts, Potential Harms and Benefits

Print

HM13968 - [name] Study of Sleep in Cirrhosis

Close

Risks, Discomforts, Potential Harms and Benefits

* Describe the risks of each research procedure to participants or others. For each identified risk, provide an
assessment of the anticipated seriousness and likelihood of the risk. Some examples of possible risks include
but are not limited to

- Physical risks (e.g. bodily harms or discomforts, side effects, etc.)
- Psychological risks (e.g. emotional, mental, or spiritual harms or discomforts, changes to thoughts, beliefs, or behaviors, etc.)
- Research data risks (e.g. loss of confidentiality and privacy)
- Social or legal risks (e.g. impacts on relationships or reputation, legal or criminal justice actions for self or others, etc.)
- Financial risks (e.g. impacts on income, employability, or insurability, loss of services, etc.)
- Other risks (e.g. unforeseeable risks of experimental procedures, risks related to particular study
 designs (randomization, washout, placebo, withholding care/services, deception), etc.)

See the help text for additional guidance.

Physical risks:

a. ramelteon side effects: these include excessive sleepiness, potential to sleep drive, worsening depression, and minor risk of allergic reactions; however these risks are inherent to any insomnia treatment and these will be explained in detail to the patients before they are initiated on this with the face to face visit.

Psychological risks: minor risk of anxiety after completion of cognitive tests: to alleviate this, all subjects will be informed that these are purely collected for research. Uncovering of risk of suicide through BDI will be dealt with by sending patients to the emergency room. Socio-leaal risks: none

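### No recall period is set for the repeated PSQI; under its usual past-month wording, about half of the post-treatment window precedes treatment even at day 15

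*Combined protocol and SAP*

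**What the plan says.** The specific aims in the Research Description name sleep quality among the outcomes. Item 3 (background) says that the effect of ramelteon will be studied "on the sleep quality (using quesitonnaires and sleep diaries) and duration on these patients with cirrhosis".

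Item 4 lists the screening procedures. After a general entry for sleep questionnaires come the Berlin, STOP-Bang and Epworth instruments and the "Pittsburgh sleep quality index (PQSI").

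The Ramelteon Therapy part of item 4 limits the course: "Patients will be asked to complete a medication and sleep diary for the duration of the drug therapy which will be a maximum of 15" (the figure is in days). It then sets the repeat assessment: "Within 15 days of drug initiation, the patients will be asked to complete the sleep questionnaires again", together with cognitive testing. It gives no fixed day and no minimum number of treated nights.

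Nowhere does the document state a recall period for the PSQI, name a modified version, or tell patients to rate only nights on treatment. The diary is described for the treatment period only; no pre-treatment diary appears.

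**The concern.** A questionnaire that looks back further than the treatment has lasted mixes nights before the drug with nights on it. The design is single-arm and pre-post, so the change in score is the treatment estimate, and no control group is described against which a diluted change could be judged. A null PSQI result could mean that the drug did nothing, or that the form was largely describing untreated sleep.

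This is separate from loose visit timing. It remains if every patient takes the full course and is seen on the last day, because a month-long window is about twice the longest course allowed.

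The diary does not fill the gap, since no baseline diary is described for comparison. Fitbit materials and the return of a device are mentioned under the uploaded documents and Compensation, but no Fitbit measure of sleep quality is defined.

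**Working it through.** The plan gives no figure on this point, so there is none to reproduce. The sample-size figures under Study Population, item 3, concern slow-wave sleep and are not inputs here.

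**Inputs**
- *d*, nights on drug when the form is completed: at most 15 (item 4, Ramelteon Therapy).
- *W*, nights in the recall window: not in the document. Assumed to be one month, with 28, 30 and 31 nights shown.

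**Share of the window that precedes treatment**, with the form completed while the patient is still on drug: U = 1 − d/W.

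| Nights on drug (d) | W = 28 | W = 30 | W = 31 |
|---|---|---|---|
| 15 | 13/28 = 46% | 15/30 = 50% | 16/31 = 52% |
| 14 | 14/28 = 50% | 16/30 = 53% | 17/31 = 55% |
| 10 | 18/28 = 64% | 20/30 = 67% | 21/31 = 68% |
| 7 | 21/28 = 75% | 23/30 = 77% | 24/31 = 77% |

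The first row is the most favourable case that the plan permits. More generally, any window longer than 15 nights must include some untreated nights.

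**From window to score.** If every recalled night counted equally, a true change D would appear as D × d/W. With d = 15 and W = 30 this is 0.5 D, so an illustrative 3-point improvement would show as 1.5 points. At d = 7 it is 7/31 to 7/28, or 0.23 D to 0.25 D. The PSQI is not a simple mean over nights, so these values are illustrations.

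If a treated (more recent) night counts k times as much as an earlier one, the visible fraction is kd/(kd + W − d). At d = 15 and W = 30 this equals k/(k + 1), which exceeds one half whenever k is above 1. Equal weighting therefore gives no upper limit on the change that would be seen.

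**Overlap with baseline.** Compensation, item 1, has a single payment line for "Screening and initiation of rametteon visit". If these are one visit, the untreated nights in a month-long post-treatment window are nights that the baseline form already covered. In the 15/30 case, 15 nights would be described by both forms.

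**Check of a shorter window.** For the past 7 nights, U = 1 − d/7 when d is below 7, and 0 from the seventh treated night. After 3 treated nights U is still 4/7 = 57%. A shorter window therefore works only with a minimum number of treated nights before the form is completed.

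**The case against.** The strongest objection is that the deciding figure is not in the document. The past-month wording is an assumption, and the 28-to-31-night range varies only the length of a month; it does not test whether the window is a month at all. The questionnaire is not reproduced. The document list under Data Confidentiality and Storage shows at least one instrument, the Sickness Impact Profile, held as a separate upload, so a modified PSQI header could exist on a form that is not shown. This stands, and it makes the point conditional. It does not remove it: an instrument named without qualification will normally be given in its usual form, and the plan says nothing to prevent that.

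Second, repetition of the PSQI is inferred from the reference to the sleep questionnaires. That is the natural reading, but it is not stated. Nor is the PSQI named as a primary or secondary endpoint.

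Third, a reader might infer that half of the post-treatment *score* describes untreated sleep, or that a 3-point improvement could show as no more than 1.5 points. The documents do not support either statement. The arithmetic gives a share of the recall window, and patients may weight recent nights more.

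Fourth, dilution biases towards no effect and would not create a false benefit. That is correct, and it limits the harm to a missed or understated change.

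**Conclusion.** The point holds in conditional form. If the PSQI is repeated, as the text implies, and carries past-month wording, 46% to 52% of its post-treatment window precedes treatment at the latest visit allowed, and 75% to 77% at day 7. The pre-post change is then likely pulled towards zero by an amount that cannot be fixed from the documents.

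The conclusion rests on three assumptions: the window is 28 to 31 nights; the form is unmodified; and it is completed while the patient is still on drug. The percentages need no assumption about how nights are weighted; any figure for the loss in score does.

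A reader might also infer that the study's power is compromised. It is not affected by this point: the sample size is based on slow-wave sleep present or absent, and the PSQI plays no part in it. The consequence is confined to the sleep-quality aim. This is a cheap improvement worth making and does not undermine the whole plan.

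**What to change.** - At both the screening and post-ramelteon visits, give the PSQI with one identical, stated recall period that fits inside the course, for example the past 7 nights. Use that pair for the pre-post comparison.
- Complete the post-treatment form only when at least that many nights on drug have passed, and while the window still covers only nights on drug. Without this condition the shorter window does not secure its purpose.
- Keep the standard form at screening, to describe the population.
- Leave the treatment schedule unchanged.
- If the form in use already has a window that fits inside the course, state this in the protocol; no other change is then needed.

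The cost is a reworded questionnaire header, a second short form at screening, and a sentence or two in the protocol on the recall period and when the form is completed. The downside is that a shortened window modifies the usual form, and its scores are less comparable with published past-month values. The standard form kept at screening offsets this only for the baseline description.

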View	FitBit Training 2	Help article_What should I know about sleep tracking_ pdf	0.01	011012010	[name]	Other	Yes
View	FITbit Training	Help article_ How do I track my sleep_ pdf	0.01		[name]	Other	Yes

Date: Tuesday, March 2, 2021 3:58:08 PM ID: HM13968

Print	Close
-------	-------

View: SF - Types of Sites

HM13968 - [name] Study of Sleep in Cirrhosis

Types of Sites

- 1.* Select which of the following accurately describes this study
- Not Multi-site Study
 Multi-site Study [multiple sites implementing the same protocol] VCU Lead
 Multi-site Study [multiple sites implementing the same protocol] Non-VCU Lead

2.* Select all sites where study interventions or interactions will occur and/or identifiable data will be held

	~	VCU Site		
	Non-VCU Site (VCU Investigators are conducting/overseeing the conduct of the study)			
		Non-VCU Site under the oversight of a Non-VCU PI		
~				

3. * Is there a community partner in this research study

● No

Date: Tuesday, March 2, 2021 3:58:44 PM

ID: HM13968

Print	Close

View: SF - Study Population

HM13968 - [name] Study of Sleep in Cirrhosis

Study Population

1.* Provide the total number of individuals at VCU, and at other sites under the VCU IRB, that

- 1. May participate in any study interaction or intervention (including screening, consenting, and study activities) AND/OR
- 2. You may obtain any data/specimens about (regardless of identifiability)

See the help text for additional guidance.

50

- 2. If this is a multi-Center Project, what is the total anticipated number of subjects across all sites
- 3. * Provide justification for the sample size

For the study of the impact of Ramelteon on SWS in cirrhotic patients, we are planning a pre-post study on the dichotomous outcome of SWS yes/no. If we assume the the success-failure proportion (cirrhotics who experienced SWS no longer experience SWS after treatment) is 1E-1 and the failure-success proportion (cirrhotics who did not experienced SWS experience SWS after treatment) is 0.50, then a sample size 14 is required to achieve a power of at least 80%. A sample size of 20 under the same assumption yields a power of 97%. We will use a McNemar Exact Conditional Test for this analysis. To account for dropouts and those who do not wish to participate in the treatment part of the study, we will enroll 50 cirrhotic patients.

4. * List the study inclusion criteria

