- 9. * Describe criteria for withdrawing an individual participant from the study such as safety or toxicity concerns, emotional distress, inability to comply with the protocol, etc. if they are diagnosed to have sleep apnea on the initial visit, since ramelteon will not work.
- 10. * Summarize any pre-specified criteria for stopping or changing the study protocol due to safety concerns none

11. Where appropriate, discuss provisions for ensuring necessary medical, professional, or psychological intervention in the event of adverse events to the subjects We have the trained staff in psychology, hepatology and sleep medicine to deal with any adverse events that potentially may occur during this study. The team works together with a potential subject and is in contact constantly with the CRSU to evaluate any potential issues.

12.* Describe any potential for direct benefits to participants in this study Sleep quality is a major concern in patients with cirrhosis and this impacts their quality of life immensely. Patients with sleep problems are not able to function normally and this is often mistaken for hepatic encephalopathy. This leads to unnecessary treatments and can in turn worsen their guality of life. A study with treatment with an FDA-approved medication, will be able to identify and possibly correct the underlying sleep disturbances both pathophysiologically as well as therapeutically. The minor risk to confidentiality and privacy and adverse effects of ramelteon are low compared to the potential

benefits of elucidating the mechanism and treatment options for these patients and potentially improve their QOL.

13. Describe the scientific benefit or importance of the knowledge to be gained Sleep quality is a major concern in patients with cirrhosis and this impacts their quality of life immensely. Patients with sleep problems are not able to function normally and this is often mistaken for hepatic encephalopathy. This leads to unnecessary treatments and can in turn worsen their quality of life. A study with treatment with an FDA-approved medication, will be able to identify and possibly correct the underlying sleep disturbances both pathophysiologically as well as therapeutically. The minor risk to confidentiality and privacy and adverse effects of ramelteon are low compared to the potential

benefits of elucidating the mechanism and treatment options for these patients and potentially improve their QOL

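### Does giving the repeat sleep questionnaires only a latest day let untreated nights spoil the post-ramelteon score?

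*Combined protocol and SAP*

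**What the plan says.** The only operational timing rule is in Research Description, item 4, under ramelteon therapy. Patients "complete a medication and sleep diary for the duration of the drug therapy which will be a maximum of 15 days", and the repeat assessment follows: "Within 15 days of drug initiation, the patients will be asked to complete the sleep questionnaires again". Cognitive testing is repeated under the same sentence. No earliest day, fixed course length or link to the last dose is given.

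Other sections indicate where the visit falls:

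- Research Description, item 4, design statement: "This study will be divided into screening and post-ramelteon visits".
- Compensation: the patient total is described as "total payment for treatment visits and post-treatment sleep visit", and the money "will only be paid after return of the Fitbit as a lumpsum".

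The Background (Research Description, item 3) says the investigators want to study the impact of ramelteon "on the sleep quality (using quesitonnaires and sleep diaries").

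On patients who do not complete, Study Population, item 3, explains the enrolment of 50 with the words "To account for dropouts and those who do not wish to participate in the treatment part of the study". The only withdrawal criterion, in the Risks section, item 9, applies to patients "if they are diagnosed to have sleep apnea on the initial visit, since ramelteon will not work". The Epworth scale and the Pittsburgh index are named at screening. Their recall periods are not given, and the plan does not list which forms are repeated.

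**The concern.** A questionnaire that asks about recent nights measures the drug only to the extent that the patient took it on those nights. With two upper limits and no lower one, two routes let untreated nights into a score that still complies with the text. The visit may fall early in the course, so that recall reaches back before the first dose. Or the patient may stop after a week and be seen on day 15, so that recall covers nights after the last dose. A form whose recall exceeds 15 nights would include untreated nights even after a full course.

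Sleep quality is a stated aim, and this is a pre-post study with no concurrent control described. If patients with very different treated shares were pooled, a null or a positive change score would be harder to interpret. The visit day also cannot be recovered once the data are in.

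**Working it through.** The plan has no figure of its own on this point. Its calculated sample sizes (14 and 20) concern slow-wave sleep and do not enter.

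**Inputs.** From Research Description, item 4: visit day v is at most 15, and course length k is at most 15 nights. Assumed, because the documents do not say: recall R of 7, 14 or 30 nights, and example courses of 7 and 10 nights.

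**Formula.** Drug is taken on nights 1 to k, and the form is completed the morning after night v.

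treated nights = max(0, min(k, v) − max(0, v − R)); treated share = treated nights / R

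| Course k | Visit v | R = 7 | R = 14 | R = 30 |
|---|---|---|---|---|
| 15 | 15 (end of full course) | 7/7 = 100% | 14/14 = 100% | 15/30 = 50% |
| 15 | 3 (early visit) | 3/7 = 43% | 3/14 = 21% | 3/30 = 10% |
| 7 | 15 (late visit) | 0/7 = 0% | 6/14 = 43% | 7/30 = 23% |
| 7 | 7 (end of course) | 7/7 = 100% | 7/14 = 50% | 7/30 = 23% |
| 10 | 15 (late visit) | 2/7 = 29% | 9/14 = 64% | 10/30 = 33% |
| 10 | 10 (end of course) | 7/7 = 100% | 10/14 = 71% | 10/30 = 33% |

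**Reading the table.**

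1. *Early visit.* The loss is large at every recall. From day 3 to day 15 of a full course the share rises from 3/14 to 14/14 and from 3/30 to 15/30. But a day-3 visit in a continuing course is not post-ramelteon or post-treatment, so this route needs item 4's time limit to be read against the design statement and the Compensation section.
2. *Late visit after a short course.* This fits every section. Its size depends on recall. Since v cannot exceed 15, the late visit can drop at most max(0, 15 − R) treated nights from the recall period. That is one night at R = 14 (1/14, or 7 percentage points) and none at R of 15 or more. Only short recall is hit hard: at R = 7, each day of delay after a course of 7 or more nights costs 1/7, or 14 points.
3. *Recall longer than the course.* At R = 30 the best attainable share is 15/30, whatever the visit day. That is a feature of the form against the length of therapy. A visit window cannot remove it.

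**The case for a change.** The strongest case for a change is that the visit labels give an order and not a day. A patient who stops on night 7 and is seen on day 15 meets every sentence in the plan, and a 7-night form would then contain no treated night at all. Short courses are foreseeable, since therapy has only a maximum and dropouts are allowed for. The diary and Fitbit are not linked to the questionnaire scores by any stated analysis. A sentence or two would settle the day and the recall, and timing cannot be repaired later.

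Part of this stands. The text states no day, no recall period and no rule for when an early stopper is assessed. A visit after a full 15-day course but within 15 days of starting also leaves almost no slack, although a visit at day 15 satisfies both.

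The rest does not carry to a change. The dropout allowance concerns attrition and does not show that patients stop early and still return on day 15. The 0% to 100% range comes from assumed recall and course lengths. The recall wording may be on the forms, and a visit schedule may be in the consent form; neither is in the published text.

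The stronger remedies have costs of their own. Assessing early stoppers when they stop gives patients unequal follow-up, whereas a common day regardless of stopping is a legitimate choice. It also leaves any course shorter than the recall only partly treated: 3 nights assessed at their end is still 3/7 at R = 7. Analysing change by treated share, or only in fully treated patients, selects on adherence after baseline. Patients may stop because the drug fails or is poorly tolerated, so such analyses can favour responders, and without a control group that cannot be separated from a drug effect.

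**Conclusion.** No change is called for. The observation about the text is correct, but the most natural reading, one visit at the end of the course, gives a fully treated score at 7- and 14-night recall and the best attainable score (50%) at 30. What remains is unstated detail about the visit window and recall that the site and analyst would fill sensibly. The medication diary already provides the nights on drug to report beside the scores.

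When to assess early stoppers is a fair trade-off, and at recall of 15 nights or more a late visit loses no treated night. No direction of bias and no loss of power has been shown, and the slow-wave-sleep outcome is untouched.

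The conclusion rests on the visit labels meaning what they say. It would be less comfortable if many patients were in fact seen mid-course, or if many stopped early and were seen on day 15 with a 7-night form. Nothing in the documents indicates either.
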